The analyses for Haemo-QoL-A domain scores (Physical functioning, Consequence of bleeding, Role functioning) will be the same as the Total score analyses.

Additional analyses of efficacy endpoints

Correlation between FVIII activity and bleeding risk

The following analyses will be performed to investigate the correlation between FVIII activity levels and ABR:

- Using a cut-off of FVIII activity level (e.g., 5 IU/dL), each subject's data will be divided into 3 periods: baseline, from Week 5 to the first time reaching 5 IU/dL, and from the first time reaching 5 IU/dL to the end of the efficacy evaluation period. For each period, the duration of the period, the number of treated bleeds, the ABR, and the change in ABR from baseline will be listed and summarized.
- Based on the FVIII activity visit windows (Appendix 20.1 Visit Windows), median FVIII activity and total number of treated bleeds (defined in Section 13.2) will be calculated for each window for every subject. The total number of treated bleeds in each window will be plotted against the corresponding FVIII activity level to show the FVIII activity level around the time of bleeding. In addition, a negative binomial regression will be performed, using the number of treated bleeds in each window and the FVIII activity level in the window to model the relationship between the FVIII activity level and ABR. The SAS GENMOD procedure will be used where a REPEATED statement is included to account for within-subject correlation.
- ABR will be summarized in subgroups of subjects determined by the FVIII activity levels measured at Weeks 23-26, Weeks 49-52, Week 104, as well as by the peak FVIII activity levels.

Joint analysis of ABR and exogenous FVIII/emicizumab use

Per the study protocol, subjects will discontinue their regular prophylactic FVIII treatment regimen starting Week 5 post the day of BMN 270 infusion and switch to an episodic treatment schedule. In addition, subjects who experience recurrent bleeding episodes may resume their prior FVIII prophylaxis or start prophylactic emicizumab treatment. Because ABR and exogenous FVIII/emicizumab use are not independent, the following analyses will be performed to jointly assess ABR and exogenous FVIII/emicizumab use:

- Paired analysis of ABR and exogenous FVIII/emicizumab use in each of the efficacy evaluation periods defined in Section 13.1. This analysis enables the interpretation of ABR in the context of exogenous FVIII/emicizumab use.

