13.1 Efficacy Evaluation Periods

To avoid breakthrough bleeding, subjects only discontinued exogenous prophylactic FVIII replacement therapy after 4 weeks following infusion of BMN 270. Four weeks represents the time by which endogenous production of FVIII following gene transfer is expected to be efficacious, based on earlier results. For the purpose of primary data analysis, the efficacy evaluation period for

- Efficacy endpoints such as ABR, number of treated bleeds, annualized FVIII utilization, annualized FVIII infusions and PROs: will be defined as starting from Week 5 post-BMN 270 dosing (Study Day 33) or 3 days after the end of FVIII prophylaxis, whichever is later, until subjects complete the study, reach the last visit by data cutoff for the analysis, or withdraw from the study (ETV), whichever is the earliest.
- Efficacy endpoint of FVIII activity based on chromogenic substrate assay: will be defined as starting from Week 5 post-BMN 270 dosing (Study Day 33) until subjects complete the study, reach the last visit by data cutoff for the analysis, withdraw from the study (ETV) (FVIII activities post withdrawal will be imputed to be 0 IU/dL through the data cutoff date for the analysis), or resume routine FVIII prophylaxis (should that occur) (Restart of FVIII prophylaxis is defined as the first usual FVIII prophylaxis administered at least once a week for ≥ 4 consecutive weeks), whichever is the earliest.

Study 270-301 Statistical Analysis Plan

- Efficacy endpoint of FVIII activity based on one-stage assay: will be defined as starting from Week 5 post-BMN 270 dosing (Study Day 33) until subjects complete the study, reach the last visit by data cutoff for the analysis, withdraw from the study (ETV) (FVIII activities post withdrawal will be imputed to be 0 IU/dL through the data cutoff date for the analysis), or resume routine FVIII prophylaxis or start emicizumab prophylaxis (should that occur) (Start of emicizumab prophylaxis is defined as the first emicizumab injection among 2 or more emicizumab injections administered within 31 days), whichever is the earliest.

For the purpose of supportive data analyses, the efficacy evaluation period for

- Efficacy endpoint of FVIII activity: will be defined as from BMN 270 infusion to until subjects complete the study, reach the last visit by data cut-off for the analysis, or withdraw from the study (ETV), whichever is the earliest.

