- Efficacy endpoints such as ABR, number of treated bleeds, annualized FVIII utilization, annualized FVIII infusions: will be some of the efficacy evaluation periods listed in [Table 13.1.1](#). In addition, descriptive summary will be provided in Weeks 1-4 and Week 1-end of FVIII prophylaxis (defined as end of week 4 post-BMN 270 infusion or 2 days after end of FVIII prophylaxis, whichever is later).

Time to discontinuation of FVIII prophylaxis post-BMN 270 infusion and duration of efficacy evaluation period for primary analysis of primary and secondary efficacy endpoints will be summarized.

[figure not shown]

Table 13.1.1: Efficacy Evaluation Periods for Analyses of Primary and Second-Ranked Secondary Efficacy Endpoints

Efficacy Evaluation Period	Start Point	End Point	Analysis
Post-FVIII prophylaxis period	Start of Week 5 post-BMN 270 infusion or 3 days after end of FVIII prophylaxis, whichever is later	Last visit by data cut-off	Primary, t-test
Post-FVIII prophylaxis – week 104	Start of Week 5 post-BMN 270 infusion or 3 days after end of FVIII prophylaxis, whichever is later	Last visit by data cut-off or end of Week 104 post-BMN 270 infusion, whichever is earlier	Supportive, t-test
Post-FVIII prophylaxis – restart of prophylactic treatment up to Week 104	Start of Week 5 post-BMN 270 infusion or 3 days after end of FVIII prophylaxis, whichever is later	Last visit by data cut-off, end of Week 104 post-BMN 270 infusion or 1 day before restart of prophylactic treatment, whichever is earlier	Supportive, t-test
Post-FVIII prophylaxis – restart of prophylactic treatment up to last visit	Start of Week 5 post-BMN 270 infusion or 3 days after end of FVIII prophylaxis, whichever is later	Last visit by data cut-off or 1 day before restart of prophylactic treatment, whichever is earlier	Supportive, t-test

Note: end of FVIII prophylaxis is defined as last usual FVIII prophylaxis not followed by another usual FVIII prophylaxis for at least 28 days.

Restart of prophylactic treatment means restart of FVIII or start emicizumab prophylaxis. Restart of FVIII prophylaxis is defined as the first usual FVIII prophylaxis administered at least once a week for ≥ 4 consecutive weeks. Start of emicizumab prophylaxis is defined as the first emicizumab injection among 2 or more emicizumab injections administered within 31 days.

Study 270-301 Statistical Analysis Plan

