13.3.4 Correlation between FVIII Activity and Bleeding Risk

FVIII activity is widely acknowledged to be a key aspect of hemophilia A and a valuable indicator of patients' status, while annualized bleeding rate has been traditionally used as the primary clinical endpoint for replacement therapy. The correlation between FVIII activity level and bleeding risk has been researched, showing that increases in FVIII activity levels are predictably associated with a decreased number of annual bleeds ([den Uijl, 2011](#)). The following analyses will be performed to explore the relationship between measured FVIII activity and bleeding in this study.

- Using a cut-off of FVIII activity level, e.g., 40 IU/dL, each subject's data will be divided into 3 periods: baseline, from Week 5 to the first time reaching 40 IU/dL, and from the first time reaching 40 IU/dL to the end of efficacy period. For each period, the duration of the period, the number of bleeds, the ABR, and the change in ABR from baseline will be listed and summarized. ABR will also be estimated using negative binomial regression modelling number of treated bleeds vs period with period duration as the offset, repeated within subject. The analysis will be performed using various cut-off, such as 5, 15, 25, 30, 40 IU/dL.
- Based on the FVIII activity visit windows ([Appendix 20.1 Visit Windows](#)), median FVIII activity and total number of treated bleeds (defined in [Section 13.2](#)) will be calculated for each window for every subject. The total number of treated bleeds in each window will be plotted against the corresponding FVIII activity level to show the FVIII activity level around the time of bleeding. A negative binomial regression will be performed, modelling number of bleeds in each window vs. FVIII activity in the window, repeated within subject (the "repeated" term may be removed in case of convergence difficulty due to small sample size). The analysis will be done for FVIII activity measured by one-stage clotting assay and chromogenic assay separately. The same analyses will be conducted for treated joint bleeds.
- ABR will be summarized in subgroups of subjects determined by the FVIII activity levels as measured at Weeks 23-26, Weeks 49-52, Week 104, as well as by the peak FVIII activity levels.

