For comparison purposes, similar analyses will be performed to assess the natural decline of FVIII activity while subjects are on or off immunosuppressants. Changes in FVIII activity levels between 4 weeks before and 4 weeks after Week 20, 24, 28, et al. will be plotted separately for subjects who ever or never received immunosuppressant therapy.

The above analyses will be repeated for select concomitant medications (e.g., lamivudine) to assess the impact of such on FVIII expression in the mITT subjects who have discontinued them before the data cut-off date for the 2-year analysis.

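### The FVIII cut-off analysis in Section 13.3.4 compares time before and after first reaching a level, not bleeding above and below it, and its start and end points do not match the SAP's ABR periods

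*SAP*

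**What the plan says.** Section 13.3.4 sets out to "explore the relationship between measured FVIII activity and bleeding in this study". Its first bullet forms three periods per subject: baseline, then "from Week 5 to the first time reaching 40 IU/dL, and from the first time reaching 40 IU/dL to the end of efficacy period". A negative binomial model is fitted to these periods, "modelling number of treated bleeds vs period with period duration as the offset, repeated within subject". Several levels are used: "The analysis will be performed using various cut-off, such as 5, 15, 25, 30, 40 IU/dL". The synopsis has the same split with 5 IU/dL as its example, the last period running "from the first time reaching 5 IU/dL to the end of the efficacy evaluation period".

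Other parts of the SAP bear on this:

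- **Start of ABR time.** Section 13.1 defines it as "starting from Week 5 post-BMN 270 dosing (Study Day 33) or 3 days after the end of FVIII prophylaxis, whichever is later", and every row of Table 13.1.1 has "Start of Week 5 post-BMN 270 infusion or 3 days after end of FVIII prophylaxis, whichever is later". The time-to-first-treated-bleed formula in Section 13.3.8 and the ABR windows in Appendix 20.1 follow the same later-of rule.
- **Expected decline.** Section 13.3.7 plans analyses "to assess the natural decline of FVIII activity while subjects are on or off immunosuppressants", and Section 13.3.2 summarises the change between maximal activity and Week 104.
- **Other bullets of Section 13.3.4.** The second bullet regresses bleeds in each visit window on FVIII activity in that window. The third summarises ABR by FVIII level at set times and by peak.

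**The concern.** There are three defects in the first bullet.

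1. **No exit.** Once a subject has reached the cut-off, all later time and bleeds belong to the last period, whatever FVIII does afterwards. A subject who touches 40 IU/dL once and then falls to 4 IU/dL stays in the period after reaching 40. The SAP expects activity to decline, so this is foreseeable.
2. **Start.** Week 5 is unconditional. A subject still on FVIII prophylaxis after Day 33 contributes prophylaxis-covered days that the SAP's ABR periods leave out.
3. **End.** The text does not say which efficacy period's end applies, so it is open whether time after restart of FVIII prophylaxis, or after start of emicizumab, is counted.

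This is the only bullet that fits a model at named cut-offs. Readers are likely to take its output as ABR at or above a level against ABR below it, and to look there for a level that protects. The periods as defined cannot supply that.

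**Working it through.** The SAP states no figure for this analysis, so there is nothing to reproduce. The check compares definitions and then shows by arithmetic how far a mixed period can move.

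**Definitions compared**

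| Source | Start | End |
|---|---|---|
| 13.3.4, first bullet | Week 5 | End of an unnamed efficacy period |
| 13.1, ABR (primary) | Later of Day 33 and 3 days after end of prophylaxis | Completion, last visit by cut-off, or withdrawal |
| 13.1, chromogenic FVIII activity (primary) | Day 33 | As above, or restart of routine FVIII prophylaxis |
| Table 13.1.1, restart rows | As ABR | At latest, 1 day before restart of FVIII or start of emicizumab prophylaxis |

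Under the ABR reading, time after both FVIII restart and emicizumab start stays in the last period. Under the chromogenic reading, FVIII restart ends it but emicizumab start does not.

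**Formula.** For a period made up of states i: ABR = Σ(days_i × ABR_i) / Σ(days_i).

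**Last period (illustration).** Assumed: cut-off first reached Day 85, follow-up to Day 730, so 730 − 85 = 645 days. ABR while above is set to 1, borrowing the post-infusion planning value in Section 4.5. ABR while below is assumed to be 3, 5 or 10.

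- Activity falls below at Day 365: 280 days above, 365 below (365/645 = 57%).
  - Below 3: (280×1 + 365×3)/645 = 2.13
  - Below 5: (280×1 + 365×5)/645 = 3.26
  - Below 10: (280×1 + 365×10)/645 = 6.09
- Activity falls below at Day 533: 448 days above, 197 below (197/645 = 31%).
  - Below 3: (448×1 + 197×3)/645 = 1.61
  - Below 5: (448×1 + 197×5)/645 = 2.22
  - Below 10: (448×1 + 197×10)/645 = 3.75

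Classifying days by current activity returns 1.00 each time. If the period before reaching also has ABR 3, the first case turns a true ratio of 3/1 = 3.0 into 3/2.13 = 1.41.

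**Middle period (illustration).** Assumed: cut-off reached Day 85, so 85 − 33 = 52 days. ABR up to the Section 13.1 start is 3.5, the planning value on prophylaxis in Section 4.5. The true ABR off prophylaxis is assumed to be 1 or 10.

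- Prophylaxis ends Day 54, ABR time starts Day 57: 24 of 52 days (46%) precede that start.
  - True 1: (24×3.5 + 28×1)/52 = 2.15
  - True 10: (24×3.5 + 28×10)/52 = 7.00
- Prophylaxis ends Day 68, ABR time starts Day 71: 38 of 52 days (73%) precede it.
  - True 1: (38×3.5 + 14×1)/52 = 2.83
  - True 10: (38×3.5 + 14×10)/52 = 5.25
- Prophylaxis ends by Day 30: no effect.

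The period's ABR is pulled towards the on-prophylaxis rate, so it rises or falls according to which rate is higher.

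**The case against.** The strongest reply is that the section does not depend on this bullet. The second bullet models bleeds on FVIII in the same window, so a fall from 40 to 4 IU/dL is reflected there, for both assays. That stands and limits the damage. It does not repair the first bullet: the regression gives no ABR at named cut-offs and states no exclusion of prophylaxis-covered time.

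The SAP also never labels the periods as above and below. Before and after first reaching a level is a legitimate description of a subject's course. That stands too, which is why the split can stay as a descriptive summary. It does not answer the section's stated aim, which concerns measured activity.

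The Week 5 start matches the chromogenic FVIII activity period in Section 13.1, and the version 2.0 change of start is recorded in Section 19 for the primary analysis of ABR, utilization and infusions, not expressly for Section 13.3.4. If the ABR period was meant, keeping time after restart is consistent with the treatment-policy strategy in Section 13.2.1. These points show that the text may be deliberate, but also that it has more than one reading. The bullet estimates ABR, and its start differs from the SAP's other ABR periods without a reason given.

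A reader might go further and infer that both defects bias towards no relationship, so that every cut-off's ABR is wrong in the same direction. The documents do not support this. The middle-period arithmetic moves both ways, and time after restart, if counted, could lower the last period's ABR.

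**Conclusion.** The point holds as a defect of definition in an exploratory analysis. The cut-off ABRs mix different FVIII and treatment states by an amount that cannot be found from the SAP, which gives no counts of subjects who fall back below a cut-off, stop prophylaxis after Day 33, or restart.

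Decline dilutes the before/after contrast, provided bleeding is higher at low FVIII. Prophylaxis-covered time can act in either direction. The figures 1.61 to 6.09 against 1.00, and 2.15 to 2.83 against 1 or 5.25 to 7.00 against 10, rest on assumed days and rates and show only that the effect can be material. Subjects who stay above the cut-off after reaching it and stopped prophylaxis by Day 30 are unaffected, unless they later restart prophylactic treatment.

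The primary endpoint and the nine-step testing sequence in Section 13.7 are not touched. A correction is still worthwhile, because this is the output most likely to be read as showing a protective level.

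**What to change.** In the first bullet of Section 13.3.4 and its counterpart in the synopsis:

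1. Start post-infusion time at the later of Day 33 and 3 days after the end of FVIII prophylaxis, as in Table 13.1.1.
2. Name the end point. Use the existing Table 13.1.1 period that ends 1 day before restart of prophylactic treatment; its version up to last visit keeps the same follow-up limit as the primary ABR period.
3. For each cut-off, classify each day as at or above, or below, by the median FVIII of its current visit window. Name the assay. Omit the overlapping Week 23–26 window of Appendix 20.1 so that no day is counted twice.
4. Fit the planned negative binomial model to bleeds by status, with days in each status as the offset and the repeated-subject term kept.
5. Keep the first-crossing split as a descriptive summary, labelled as before/after first reaching the cut-off.

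The cost is SAP wording and moderate reprogramming on data already windowed; no new data are needed. The downside is that some subjects will contribute several short segments per status.

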13.3.5 Joint Analysis of ABR and Exogenous FVIII/Emicizumab Use

Per the study protocol, subjects will discontinue their regular prophylactic FVIII treatment regimen starting Week 5 post the day of BMN 270 infusion and switch to an episodic treatment schedule. In addition, subjects who experience recurrent bleeding episodes may resume their prior FVIII prophylaxis or start prophylactic emicizumab treatment. Because ABR and exogenous FVIII/emicizumab use are not independent, the following analyses will be performed to jointly assess ABR and exogenous FVIII/emicizumab use:

- Paired analysis of ABR and exogenous FVIII/emicizumab use in each of the efficacy evaluation periods defined in Section 13.1. This analysis enables the interpretation of ABR in the context of exogenous FVIII/emicizumab use.
- Summary of ABR in subgroups of subjects determined by the level of exogenous FVIII/emicizumab use:
 - Subjects who did not resume exogenous FVIII/emicizumab prophylaxis
 - Subjects with zero FVIII infusions
 - Subjects with at least one FVIII infusion
 - Subjects who resumed FVIII/emicizumab prophylaxis
 - Subjects who resumed FVIII prophylaxis
 - Subjects who resumed emicizumab prophylaxis

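### The exploratory window-level regression of bleeds on FVIII activity (SAP 13.3.4, second bullet) does not exclude or adjust for time on prophylaxis, which tends to understate bleeding risk at low FVIII

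*SAP*

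**What the plan says.** Section 13.3.4, second bullet, takes the FVIII windows of Appendix 20.1. Median FVIII activity and the number of treated bleeds "will be calculated for each window for every subject", the pairs are plotted, and a negative binomial regression is fitted, "modelling number of bleeds in each window vs. FVIII activity in the window, repeated within subject". It is run for each assay and repeated for treated joint bleeds. The synopsis describes the same analysis for treated bleeds. Neither text names an evaluation period, a prophylaxis or emicizumab covariate, or an offset.

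Appendix 20.1 lists Weeks 1-4 (Days 2 to 32) as one of these windows and continues through follow-up without a stop at restart of prophylaxis.

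Section 13.1 says that "subjects only discontinued exogenous prophylactic FVIII replacement therapy after 4 weeks following infusion of BMN 270", and that "Four weeks represents the time by which endogenous production of FVIII following gene transfer is expected to be efficacious". Section 13.3.5 adds that subjects with recurrent bleeds may go back to FVIII prophylaxis or start emicizumab, and introduces its own joint analyses with "Because ABR and exogenous FVIII/emicizumab use are not independent".

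**The concern.** The regression is meant to describe how often subjects bleed at a given level of FVIII. A window spent on prophylaxis does not answer that question. Its FVIII value, once values soon after an infusion are excluded, mainly reflects endogenous expression, while its bleed count reflects the treatment.

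Such windows are likely to sit at the low end of the FVIII scale. In Weeks 1-4 expression is still building up, and restart follows recurrent bleeding. Entered as if unprotected, they pull down the apparent bleeding rate where a reader would most want to know it. The first bullet of the same section starts its post-infusion time at Week 5 ("from Week 5 to the first time reaching 40 IU/dL"); the second bullet has no such start.

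**Working it through.** **1. Does another provision already exclude protected time?**

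- *Primary FVIII period (13.1).* It runs from Day 33 to restart of routine FVIII prophylaxis, but 13.3.4 does not cite it. If it did apply, it would still start at Day 33 when prophylaxis ended later. Its chromogenic form does not stop at the start of emicizumab; only the one-stage form does.
- *Supportive FVIII period (13.1).* It "will be defined as from BMN 270 infusion to until subjects complete the study, reach the last visit by data cut-off for the analysis"; early withdrawal also ends it. It keeps Weeks 1-4 and all time after restart.
- *72-hour rule (13.3).* It drops FVIII values taken within 72 hours of exogenous FVIII. A window left with no value falls out if only observed values are used. A window that keeps one value keeps its whole bleed count. Emicizumab is not covered.
- *Intermittent-missing rule (5.6).* If applied here, it would refill an emptied window with the smaller neighbouring value. 13.3.4 does not say whether it applies.

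So no stated rule removes all protected time under any reading.

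**2. How many windows?** Appendix 20.1 has 27 post-infusion FVIII windows through Week 104 (13 from Weeks 1-4 to Weeks 49-52, the overlapping Weeks 23-26 row, and 13 from Week 56 to Week 104). Weeks 1-4 is 1/27 = 3.7% of them. Its share of the low-FVIII windows is probably larger, but the document does not give it.

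**3. Size of the distortion.** The SAP states no figure for this regression, so there is none to reproduce. Let the unprotected rate at low FVIII be λ, the protected rate rλ, and the protected share of low-FVIII time p. Then

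observed rate = (1 − p)λ + p·rλ = λ[1 − p(1 − r)].

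Section 4.5 gives mean annualized bleeding rates (ABRs) of about 3 to 6 on prophylaxis and 30 to 60 on episodic treatment. Hence r = 3/30 = 6/60 = 0.1, with extremes 3/60 = 0.05 and 6/30 = 0.2. The share p is assumed.

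| p | Understatement, r = 0.05 | r = 0.1 | r = 0.2 |
|---|---|---|---|
| 5% | 4.75% | 4.5% | 4% |
| 10% | 9.5% | 9% | 8% |
| 25% | 23.75% | 22.5% | 20% |
| 50% | 47.5% | 45% | 40% |

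This is the crude rate at low FVIII, and it assumes that protected and unprotected low-FVIII windows are otherwise alike.

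**4. Effect on the fitted curve.** A small simulation used 112 subjects, 26 four-week windows, an unprotected rate of 30/(1 + FVIII) per year, assumed FVIII curves, no 72-hour exclusion and 15 replicates per setting. It compared all windows with unprotected windows only.

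| r | Restarts among late low expressers | Crude ABR below 5 IU/dL, all vs unprotected | Fitted ABR at zero FVIII, all vs unprotected |
|---|---|---|---|
| 0.1 | none | 10.2 vs 17.0 | 5.60 vs 6.42 |
| 0.1 | 70% | 7.1 vs 11.5 | 4.62 vs 5.25 |
| 0.5 | none | 12.0 vs 12.4 | 6.32 vs 5.18 |
| 0.5 | 70% | 13.4 vs 12.7 | 6.76 vs 4.90 |

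At r = 0.1 the fitted rate is lower by 1 − 5.60/6.42 = 13% and 1 − 4.62/5.25 = 12%, much less than the crude rate. At r = 0.5 there is no consistent understatement: a protected window at zero FVIII still bleeds at 0.5 × 30 = 15 per year, above the fitted value. With no restarts the unprotected-only result should not depend on r, yet it moves from 6.42 to 5.18. Fifteen replicates are therefore noisy, and only the comparison within a row is informative.

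**The case against.** The strongest reply is that the second bullet is silent on its period, so reading in every window is only one interpretation. Section 13.1 has a primary FVIII period starting at Week 5, and Section 13.3.2 names the supportive period when it wants it. The 72-hour rule would also empty many on-prophylaxis windows. Finally, the analysis is one of several that Section 13.3.4 presents as exploring the relationship, and Section 13.3.5 looks at bleeding and exogenous treatment together.

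Much of this stands as a limit on size and importance. It does not settle the point. The literal text covers each window and every subject, and the most favourable period still admits chromogenic windows on emicizumab and prophylaxis that ended after Day 33. The analyses in 13.3.5 are summaries of ABR by treatment use and do not correct this regression.

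A reader might infer more: that a definite bias can be quoted, that most low-FVIII windows are protected, or that this is the SAP's principal estimate of how bleeding depends on FVIII. The document supports none of these. It gives no FVIII distribution, no prophylaxis frequency and no restart rate, and it ranks no analysis in 13.3.4 above the others.

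**Conclusion.** The point holds as a defect in an exploratory analysis. As written, the second bullet can mix protected and unprotected time with nothing in the model to separate them. The expected direction is understatement of bleeding risk at low FVIII. That direction depends on strong protection (r near 0.1), which the ranges in Section 4.5 imply; at r = 0.5 it is not assured.

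The size is open. The crude rate at low FVIII would be about 4% to 48% too low over the assumed p of 5% to 50% and r of 0.05 to 0.2. The fitted curve moved less, about 12% to 13% in the simulation at r = 0.1, before any loss of windows to the 72-hour rule. None of these is an expected value for this trial. The primary endpoint, the testing sequence and alpha are not touched.

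**What to change.** Restrict the plot and regression in the second bullet, the synopsis version and the treated joint bleed version to time inside the last period of Table 13.1.1. That period starts at Week 5 or 3 days after prophylaxis ends, whichever is later, and stops the day before restart of FVIII prophylaxis or start of emicizumab, or at the last visit. Apply it to both assays. Take both the FVIII median and the bleed count from the retained days only, use log retained days as the offset (needed because partial windows differ in length, and none is stated now), and say whether windows without a measured value are omitted. Keep the all-window version as a sensitivity analysis.

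The programming cost is a data filter and an offset. The data cost is the Week 1-4 window, any later windows before prophylaxis ended, and all time after restart, so more than one window for some subjects. Follow-up then stops at an event that may itself follow bleeding, which should be stated with the results. One-time prophylaxis, or courses too short to meet the restart definition, would remain in the data.
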